6.2. Efficacy Procedures

Not applicable.

6.3. Pharmacokinetic Procedures

Plasma samples will be collected to determine concentration of apaglutide. Samples will be collected for 312 hours post-dose administration. The specific times for all PK samples are detailed in [Table 1](#). For post apaglutide PK sampling, up to 20 mins post dose, a time window of ± 1 minute is permitted. Thereafter, a time window of $\pm 5\%$ of elapsed time post apaglutide dosing is permitted. Outside these time points a protocol deviation should be recorded

Pharmacokinetics will not be assessed for metabolites because:

- No metabolites have known or suspected activity
- No metabolites have been identified as toxic in pre-clinical studies, which could be affected by hepatic function
- No metabolites are suspected to reach active/toxic levels if the accumulation of the metabolites is substantial

Apaglutide will be quantified in human plasma samples using a fully validated liquid chromatography mass spectrometry-based method, with a lower limit of quantification of 1 ng/mL and an upper limit of 200 ng/mL.

At time points when PK blood samples, vital signs, and ECG recordings coincide, the following order is to be maintained: ECG recording, vital signs, and PK sampling.

Samples for PK analysis must always be drawn before administration of apaglutide and the exact time of PK sampling and subsequent apaglutide administration needs to be captured.

This document is proprietary to VectivBio and for restricted circulation and access only.

Details on blood volume, handling, storage, and shipment of the samples to the central laboratory will be provided in a trial-specific Laboratory Manual. It is important to document the exact time of apraglutide administration and PK sampling.

6.4. Pharmacodynamic Procedures

Not applicable.

6.5. Biomarker and Genetic Assessments

Not applicable.

6.6. Safety Procedures

The specific times for all safety assessments are detailed in [Table 1](#). For post IMP safety assessments, up to 2.5 hours post dose, a time window of ± 15 minutes is permitted. For all other time points a time window of $\pm 5\%$ of the elapsed time since doing is permitted.

6.6.1. Physical Examination

A general physical examination is conducted at time points specified in the Schedule of Events ([Table 1](#)). This must include height and weight measurement and examination of the eyes, neurological, GI, respiratory, circulatory, muscular, cardiovascular, lymphatic, ears, nose, and throat. An abbreviated physical examination will be conducted on discharge from the CRU. Additional physical examination will be performed at any time during the treatment, if clinically indicated.

This examination serves to detect obvious and severe abnormalities and will be documented in the source documents and eCRF.

6.6.2. Laboratory Assessments

Blood samples for hematology; clinical chemistry, including liver enzymes; and hemostasis and urine samples for urinalysis will be collected at the time points specified in the Schedule of Events ([Table 1](#)).

The total blood volume to be collected during this trial will not exceed 200 mL for each subject. For subjects with a positive virology/serology result for hepatitis B and/or C at visit 1, an additional volume, up to a maximum of 4 mL, will be drawn for viral load assessment of hepatitis B and/or C. Repeat or unscheduled samples may be taken for safety reasons or if there were technical issues with a sample.

Blood and urine samples will be processed at the site and sent to the central laboratory for analysis. Details of handling and shipping will be described in the Laboratory Manual. Information of the clinical laboratories involved in the trial will be available in the Laboratory Manual and Site File.

This document is proprietary to VectivBio and for restricted circulation and access only.

All laboratory reports will be reviewed by the Investigator and parameters out of normal range assessed as “clinically significant” or “not clinically significant.” Clinically significant abnormal results during the trial will be appropriately followed up by the Investigator and recorded as an AE.

The following parameters will be assessed during the trial.

6.6.2.1. Hematology

- Erythrocytes
- Hematocrit
- Hemoglobin
- Leucocytes, automated differential counts and percentages
- Thrombocytes (platelets)

6.6.2.2. Clinical Chemistry

- Sodium
- Potassium
- Magnesium
- Chloride
- Calcium
- Glucose
- Creatinine
- Uric acid
- Total bilirubin
- Direct bilirubin
- Triglycerides
- Cholesterol
- Alkaline phosphatase
- Creatinine phosphokinase
- Alanine aminotransferase
- Aspartate aminotransferase
- Albumin
- Total protein
- Gamma-glutamyl transferase
- Lipase

This document is proprietary to VectivBio and for restricted circulation and access only.

- Amylase

6.6.2.3. Urinalysis

A midstream, clean-catch urine specimen will be collected for dipstick analysis of:

- pH
- Leukocytes
- Protein
- Glucose
- Hemoglobin (blood)

Microscopic analysis will only be performed if results are positive or strong positive for blood, protein, or leukocytes.

6.6.2.4. Additional Parameters

Hemostasis

- Prothrombin time
- International normalized ratio (prothrombin time)

Serology (Virology)

- Human immunodeficiency virus (HIV antigen/antibody)
- Hepatitis A (anti-HAV total)
- Hepatitis B (anti-HBc and HBsAgB)
- Hepatitis C (anti-HCV)

Assessment of Viral Load

For subjects with a positive virology/serology result for hepatitis B or C, viral load will be assessed via polymerase chain reaction (hepatitis B virus DNA or HCV RNA) to ensure that viral load is undetectable.

COVID-19 Testing

All subjects will be required to undergo COVID-19 testing prior to entry to the CRU as per the Investigator site standard operating procedures. Please see [Section 13.9](#).

Pregnancy Test

A serum pregnancy test will be performed for all pre-menopausal female subjects as detailed in the Schedule of Events ([Table 1](#)). To be considered sterilized or infertile, women must have undergone surgical sterilization (bilateral tubectomy, hysterectomy or bilateral ovariectomy) or be post-menopausal (defined as at least 12 months amenorrhea without an alternative medical cause; may be confirmed with an estradiol and FSH test if there is doubt). Any pregnancies must be reported.

This document is proprietary to VectivBio and for restricted circulation and access only.

Drugs of Abuse/Alcohol

Drugs of abuse will be measured in urine/serum. These will include but are not limited to cannabinoids, amphetamines, opiates, methadone, cocaine, benzodiazepines, and barbiturates.

Alcohol will be measured using breath testing.

6.6.3. Twelve-lead Electrocardiogram

TriPLICATE 12-lead resting ECG will be recorded at the time points specified in the Schedule of Events ([Table 1](#)) using the standard equipment at the site. The procedure will be performed with the subject in a supine position after 10 minutes rest. Additional ECG monitoring will be performed at any time during the treatment, if clinically indicated. All ECG parameters, including intervals, (QRS and QT will be recorded. QT corrected according to Fridericia's formula [QTcF]) will be recorded in the eCRF.

Additionally, an overall clinical assessment of the ECG will be made and recorded as "normal," "abnormal not clinically significant," or "abnormal clinically significant." Abnormal clinically significant findings at Screening will be recorded as medical history and clinically significant new findings or worsening in ECG results during the trial must be recorded as an AE.

6.6.4. Vital Signs

Vital signs including systolic and diastolic blood pressure, heart rate, and temperature will be measured at the time points specified in the Schedule of Events ([Table 1](#)).

Systolic and diastolic blood pressure will be measured in supine position (after 5 minutes rest). Remaining vital signs will be measured in a supine position after at least 5 minutes rest. Blood pressure will be recorded in mmHg and temperature will be recorded in either centigrade or Fahrenheit.

6.7. Patient-reported Outcomes

This trial is not investigating efficacy; therefore, this is not applicable.

6.8. Pregnancy

See [Section 11.4](#).

7. LIFESTYLE AND/OR DIETARY RESTRICTIONS

The following restrictions will apply during the trial:

- Alcoholic beverages and/or alcohol containing products are not allowed 48 hours before admission to the CRU until the last scheduled evaluation and blood sample collection before discharge
- Drugs of abuse are not permitted for the entire duration of the trial
- Smoking is not permitted in the CRU. Outside smoking is permitted, but not exceeding 10 cigarettes (or equivalent) per day

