Following consent, subjects will undergo a Screening procedure to determine their suitability for trial enrollment. Screening will occur within a 28-day window before dosing. Subjects will be admitted on Day -1. On Day 1, a single SC injection of 5 mg apaglutide will be administered. The subjects will remain at the Clinical Research Unit (CRU) post-dose and either will be discharged on Day 11 or will be allowed to leave the center on Day 8 and will be asked to come back on Day 11 and Day 14 for an outpatient visit. Pharmacokinetics will be assessed on Days 1 to 8, Day 11 and Day 14. The End of Trial (EOT) visit will take place on 14 ± 2 days. Pharmacokinetics in blood samples will be assessed for 312 hours (until Day 14 inclusive). Subjects who received apaglutide (except subjects who exit from the trial early) will return to the CRU approximately 14 ± 2 days after dosing for the EOT visit where follow-up assessments will be performed according to the Schedule of Assessments ([Table 1](#)) and to determine if any AEs have occurred since the last trial visit. The planned length of the trial is up to 42 ± 2 days (from Screening through trial completion) for each enrolled subject.

Trial Population

Number of Subjects

A total of approximately 24 to 32 subjects will be enrolled if the two parts of the trial are performed. In Part 1, a total of approximately 16 subjects will be enrolled; approximately eight subjects with moderate hepatic impairment (Child-Pugh B; Cohort 1) and approximately eight subjects with normal hepatic function (Cohort 2) to ensure at least six evaluable subjects in each group. Subjects with normal hepatic function will be matched 1:1 for age (± 10 years), BMI ($\pm 15\%$), and sex (1:1) to subjects with moderate hepatic impairment.

If the decision criterion to proceed to Part 2 is met, approximately eight subjects with mild hepatic impairment (Child-Pugh A; Cohort 3) will be enrolled to ensure at least six evaluable subjects in each group. The matching will be a group matching for age, BMI, and sex, with approximately 50% of the subjects with normal hepatic function (Cohort 2) on both sides of the median for age and BMI of all subjects with hepatic

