- e. Safety laboratory assessments include chemistry, hematology, serology (screening only), and urinalysis (and microscopy, if needed) and will be performed at Screening, on Day -1, Day 2, Day 8, Day 11, and End of Trial or Early Termination visit. At Day -1, the results must have no clinically significant findings as per the Investigator's judgment to allow investigational medicinal product administration on Day 1. An optional HbA1c and TSH will be allowed at Screening, if applicable, per the discretion of the Investigator to confirm stability of concurrent medical conditions
- f. To confirm eligibility, participants must correspond to one of the following categories of the Child-Pugh score: mild, moderate, or have a normal hepatic function. The Child-Pugh assessment will only be performed in hepatically impaired subjects. Echography might be performed for small ascites.
- g. Confirmation of appropriate use
- h. This test may be performed at any other time at the discretion of the Investigator
- i. Triplicate 12-lead ECG will be performed after supine rest of 10 minutes at Screening, Day -1, Day 1 (pre-dose), Day 2 (24 hours post dose), and again on Day 8, Day 11, and End of Trial or Early Termination visit. The triplicates are performed at 1 minute intervals for 3 minutes and the average of triplicates for each parameter is calculated and used for the statistical analyses.
- j. Obtain blood pressure and heart rate measurements after at least 5 minutes of rest in a supine position. One repeat measurement may be allowed at the discretion of the Investigator
- k. Injection site reaction assessments to be assessed and recorded as an AE if present
- l. Pharmacokinetic time points will be as follows: 0 (5 minutes pre-dose), 6, 12, 24, 28, 36, 40, 48, 60, 72, 96, 120, 144, 168, 240 and 312 hours
- m. Some subjects will remain at the CRU and will be discharged on Day 11 while some others will be allowed to leave the center on Day 8 and will be asked to come back on Day 11 for an outpatient visit
- n. Changes since Screening
- o. Vital signs on Day 1 at pre-dose, 1 hour and 4-hour post dose time points. Vital Signs will be obtained within 45 minutes prior to dosing on Day 1
- p. PK sampling must be done on Day 14 (312 hours), other procedures can be completed ±2 days

This document is proprietary to VectivBio and for restricted circulation and access only.

Template no.: TMP-SOP-CD-04_1
Version no.: 2.0
Effective date: 02 Mar 2022

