Table 2 Child-Pugh Assessment System

Assessment	Points scored for Observed Findings		
	1	2	3
Encephalopathy grade ^a	none	1 or 2	3 or 4
Ascites	absent	slight	moderate
Serum bilirubin (mg/dL)	<2	2 to 3	>3
Serum albumin (g/dL)	>3.5	2.8 to 3.5	<2.8
Prothrombin time (seconds prolonged)	<4	4 to 6	>6

Child-Pugh assessment scoring system: Child-Pugh A=5 or 6 points; Child-Pugh B=7 to 9 points; Child-Pugh C=10 to 15 points

a. Assessments of encephalopathy should be based on clinical signs and symptoms; an encephalogram is not obligatory for the grading of encephalopathy. Grade 0=normal consciousness, personality, neurological examination, and electroencephalogram. Grade 1=restless, sleep disturbed, irritable/agitated, tremor, impaired handwriting, and 5 cycles per second (CPS) waves. Grade 2=lethargic, time-disoriented, inappropriate, asterixis, ataxia, and slow triphasic waves. Grade 3=somnolent, stuporous, place-disoriented, hyperactive reflexes, rigidity, and slower waves. Grade 4=unrousable coma, no personality/behavior, decerebrate, slow 2-3 CPS delta activity

Figure 2 Trial Schematic Diagram

EOT=end of treatment

^a. Some subjects will remain at the Clinical Research Unit and will be discharged on Day 11 while some others will be allowed to leave the Clinical Research Unit on Day 8 and will be asked to return for an outpatient visit on Day 11 and Day 14.

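### The alcohol restriction ends at discharge, but safety laboratory tests, including liver tests, continue to the End of Trial visit, so at least the last panel is taken without it

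*Protocol*

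**What the plan says.** Protocol Section 7 bars alcohol from 48 hours before admission "until the last scheduled evaluation and blood sample collection before discharge". The next bullet is worded differently: "Drugs of abuse are not permitted for the entire duration of the trial". The smoking bullet sets a daily limit that also applies outside the unit.

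Table 1 footnote m says that some subjects "will be discharged on Day 11 while some others will be allowed to leave the center on Day 8". The footnote to Figure 2 likewise says that some "will be allowed to leave the Clinical Research Unit on Day 8". The synopsis adds that the early leavers "will be asked to come back on Day 11 and Day 14 for an outpatient visit". No rule says who leaves when.

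Safety laboratory tests "will be performed at Screening, on Day -1, Day 2, Day 8, Day 11, and End of Trial or Early Termination visit" (Table 1 footnote e). The chemistry panel in Section 6.6.2.2 includes ALT, AST, alkaline phosphatase, GGT and bilirubin. SAP Section 9.2.1 defines baseline as the last pre-dose observation, and SAP Section 17.1.3 summarizes laboratory changes from baseline by hepatic function group and scheduled time.

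No section of either document extends the alcohol restriction past discharge.

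**The concern.** The baseline, Day 2 and Day 8 panels are taken under the restriction. At least the End of Trial panel is not, and the Day 11 panel may not be, depending on what discharge means. A late change from baseline therefore compares a restricted value with an unrestricted one.

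Liver results matter in this trial. Protocol Section 1.3.1 reports transaminase increases at a higher dose. Section 11.2.3 monitors gallbladder, biliary and pancreatic events through liver enzymes, bilirubin, lipase and amylase. SAP Table 4 names transaminase increase as an event of particular interest. With about eight subjects per group, one subject's late rise can move a group mean.

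Alcohol history is taken at Screening (Section 6.1), and the SAP lists alcohol use only among baseline characteristics (Section 13.3). Neither document requires intake after leaving the unit to be recorded, so a late rise could not readily be explained afterwards.

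**Working it through.** The plan gives no figure to reproduce, and no sample size or power figure depends on this point. The check is a timeline.

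**Inputs**
- Study day to post-dose hours: (day − 1) × 24. Day 8 = 7 × 24 = 168 h; Day 11 = 10 × 24 = 240 h; Day 14 = 13 × 24 = 312 h. These agree with the sampling times in Table 1 footnote l, which end "72, 96, 120, 144, 168, 240 and 312 hours".
- Post-dose safety laboratory time points (footnote e): Day 2, Day 8, Day 11 and End of Trial, so 4.
- End of restriction: the last evaluation and sample before discharge (Section 7). Tests done on the day of discharge are therefore still covered.

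**Unrestricted time to nominal Day 14**

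| | Discharge = Day 11 | Leaving on Day 8 counts as discharge |
|---|---|---|
| Hours to Day 14 | 312 − 240 = 72 | 312 − 168 = 144 |
| Share of 312 h | 72/312 = 23% | 144/312 = 46% |
| Hours before the Day 11 tests | 0 | 240 − 168 = 72 |
| Laboratory time points after the restriction ends | 1 of 4 (End of Trial) | 2 of 4 (Day 11, End of Trial) |

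If both kinds of leaving count as discharge, the two sets of subjects differ by 144 − 72 = 72 h.

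**Effect of the visit window.** Only the 312 h PK sample is fixed to Day 14; other End of Trial procedures may move by 2 days (footnote p).
- Window read as study Days 12 to 16 (264 to 360 h): unrestricted time before the visit is 24 to 120 h after a Day 11 discharge and 96 to 192 h after leaving on Day 8.
- Window read as 12 to 16 days after dosing (288 to 384 h): 48 to 144 h and 120 to 216 h.

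The gap is positive under every combination.

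**PK.** AUC from 0 to 168 h is complete by Day 8. Only the 240 h and 312 h samples, 2 of 15 post-dose samples, can fall after the restriction ends.

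**The case against.** **Discharge is not defined.** The documents use *discharged* for Day 11 and *allowed to leave* for Day 8. If only Day 11 is discharge, everyone is restricted to Day 11, the 46% figure falls away and subjects are treated alike. This stands, so the larger figure is conditional. The 72 h gap remains. In SAP Appendix 2 the discharge mark sits in the last column, but column positions in the extracted tables are unreliable and footnote m gives Day 8 or Day 11.

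**Lifestyle instruction is repeated.** Both schedules show a second instruction on lifestyle restrictions, under Day 8 in the SAP table as extracted. This suggests that some restrictions were meant to continue and weakens any inference that the alcohol rule was deliberately made shorter. It does not change the end date in Section 7.

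**Alcohol can be tested.** Footnote h allows a test at any other time at the Investigator's discretion. The protocol's Table 1 shows extra marks for this test that cannot be placed reliably; SAP Appendix 2 shows Screening and Day -1 only. A test can detect intake, but it does not extend the restriction.

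**The consequence is limited.** Early panels are restricted for everyone, causality assessment already weighs medical history and underlying disease (Section 11.1.2), and safety is a secondary objective analysed descriptively. The transaminase signal arose at 56.8 mg, about 11 times the 5 mg given here (56.8/5 = 11.4). All of this stands. Late liver results are harder to interpret, but not uninterpretable.

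**Stronger readings.** A reader might infer that the late PK samples and the ECGs taken "again on Day 8, Day 11, and End of Trial or Early Termination visit" are also compromised, but the documents give no basis for an alcohol effect on either. A reader might also infer bias between hepatic function groups. That would need leaving day or drinking to differ by cohort, which nothing shows. Nor do the documents support a concern about relapse: eligibility requires cirrhosis without stating an alcoholic cause.

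**Conclusion.** The point holds as a mismatch between Section 7 and the assessment schedule. At nominal timing, the restriction lapses for at least 72 of 312 post-dose hours (23%) in every subject, before 1 of 4 post-dose laboratory time points. For Day 8 leavers it is 144 h (46%) and 2 of 4, provided that leaving on Day 8 counts as discharge; only on that reading does the restriction differ between subjects.

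The consequence is confined to interpreting late liver results within the secondary safety objective. Confounding by alcohol is possible, not demonstrated. The conclusion rests on the literal end point in Section 7 and on footnote m for the day of leaving. The change is worth making because it is cheap and because intake that was never recorded is hard to reconstruct later.

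**What to change.** In protocol Section 7, end the alcohol restriction at completion of the End of Trial visit instead of at discharge, so that it matches the assessment schedule. This also removes the dependence on what discharge means. Give subjects the same end point at the lifestyle instruction already scheduled.

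Ask about alcohol intake at the existing Day 11 and End of Trial visits. List the answers, with the day of leaving the CRU, alongside the substance-use data in SAP Section 13.3.

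The cost is one sentence in the protocol, matching subject instructions, one question at two existing visits and an addition to a listing. For subjects it means about 3 more days of abstinence after a Day 11 discharge (72/24) or 6 after leaving on Day 8 (144/24). If the visit falls at the end of its window, a Day 8 leaver could have 8 days (192/24) or 9 (216/24), depending on how the window is counted.

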7.1. Contraception Requirements

7.1.1. Women of Childbearing Potential

7.1.1.1. Definition of Childbearing Potential

A woman is considered to be of childbearing potential, i.e., fertile, following menarche and until becoming post-menopausal unless permanently sterile.

Permanent sterilization methods include hysterectomy, bilateral salpingectomy, and bilateral oophorectomy.

Post-menopausal state is defined as 12 consecutive months with no menses without an alternative medical cause (ICH M3 definition).

7.1.1.2. Methods of Contraception

Women of childbearing potential must agree to practice effective contraception and to use a highly effective method of contraception during the trial and for 4 weeks after the EOT visit.

Such methods include:

- Combined (estrogen and progestogen containing) hormonal contraception associated with inhibition of ovulation (oral, intravaginal, transdermal)
- Progestogen-only hormonal contraception associated with inhibition of ovulation (oral, injectable, implantable)
- Intrauterine device
- Intrauterine hormone-releasing system
- Bilateral tubal occlusion
- Vasectomized partner, if this is their sole sexual partner

Women who do not engage in heterosexual intercourse will be allowed to join the trial without contraception following a thorough discussion with the Investigator to determine if this is feasible for the subject. The following methods are not considered acceptable methods of contraception: calendar, ovulation, symptothermal, post-ovulation methods, withdrawal (coitus interruptus), spermicides only, and the lactational amenorrhea method.

